ii) Clinical Significance	page 27
III) Research Design and Methods	page 29
IV) Protection of Human Subjects	page 33
V) Adequacy of Protection against Risks	page 35
VI) Subject Safety and Minimizing Risks	page 42
VII) Consultants	page 43
VIII) Facilities Available	page 44
IX) Appendices	page 45
X) References	page 71

I) SPECIFIC AIMS

i) Aim 1

The primary outcome is to assess the safety and toxicity profile of the combination of famotidine and oral n-acetyl cysteine in adult outpatients with newly diagnosed SARS-CoV-2 infection.

ii) Hypothesis 1

We hypothesize that the combination of famotidine and n-acetyl cysteine are a safe combination of therapies in adult outpatients with newly diagnosed SARS-CoV-2 infection.

iii) Aim 2

The secondary outcome is to assess whether certain markers (e.g., IL-1 β , IL-2, IL-6, Tryptase, Glutathione, F2-Isoprostane/Creatinine, N-methylhistamine, CAP-SYM 18, IPSS and CURB-65) are predictive of outcomes and/or treatment response.

iv) Hypothesis 2

We hypothesize that treatment with the combination of n-acetyl cysteine and famotidine in addition to the potential for reducing the primary endpoint of risk of hospitalization may also affect specific markers of infection which may prove useful surrogates for predicting the severity of the infection.

II) BACKGROUND AND SIGNIFICANCE

i) Background

N-Acetyl Cysteine (NAC) is a prodrug to L-cysteine which is a precursor to the biologic antioxidant glutathione. Administration is FDA approved for acetaminophen poisoning for which it is nearly 100% effective if given within 8 hours¹ and works through replenishing glutathione stores.²

Famotidine is a histamine-2 (H₂) receptor antagonist. Administration is approved in adult and pediatric patients 40 kg and above for the treatment of active duodenal ulcer, active gastric ulcer, symptomatic non-erosive gastroesophageal reflux disease (GERD), and erosive esophagitis due to GERD if diagnosed by biopsy. Administration is also approved in adults for the treatment of pathological hypersecretory conditions (e.g., Zollinger-Ellison Syndrome, multiple endocrine neoplasias) and for the reduction of the risk of duodenal ulcer recurrence.

There have been no studies on the use of the combination of FAM and NAC in the treatment of outpatients who test positive for SARS-CoV-2 infection.

a) Biochemical rationale

1. **Angiotensin Converting Enzyme 2 (ACE2) is SARS-CoV-2 Virus Binding Site**

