The doses to be tested for famotidine are 20 mg thrice daily, 40 mg thrice daily, 80 mg thrice daily and no famotidine. The doses to be tested for n-acetyl cysteine are 600 mg thrice daily, 1200 mg thrice daily and 1800 mg thrice daily. The dose combinations are labelled 1 through 12 and are zoned as illustrated in Figure 10. The first zone has the combination of the lowest dose of each drug. The second zone has the combination of the lowest dose of each drug with the middle dose of each drug. The dose escalation starts with the first zone and follows with the second zone and then each combination of doses in the zone next closest to the coordinate

[figure not shown]

Figure 10. Dose Combinations of N-Acetyl Cysteine and Famotidine

origin shown in figure 10. Combination doses in the same zone are tested simultaneously using block randomization to control the number of patients for each open dose. Some combinations doses may close, in which case blocked randomization is applied to the remaining open combination doses in the same zone. A modified “3+3” design¹⁷² will be used for the initial dose escalation.

To find acceptable dose levels any grade 3 or higher toxicity will be considered a dose-limiting toxicity (DLT). The modified “3+3” design proceeds as described below. Three patients receive dose level 1. Their responses determine the subsequent steps as described in the following decision rules.

- (1) If two patients (2/3) experience DLT, then we close dose level 1 and all larger doses to testing.
- (2) If no patient experiences DLT, then we designate dose level 1 as an admissible dose, and open doses in zone 2 for testing.
- (3) If only one of the first three patients (1/3) experiences DLT, then we assign three more patients to dose level 1. In this case, we assign up to six patients to this dose, and the following decision rules apply:
 - a. If only one of the six patients (1/6) experiences DLT, then we designate dose level 1 as an admissible dose, and open doses in zone 2 for testing.
 - b. If two of the six patients (2/6) experience DLT, then we designate dose level 1 as an admissible dose, and doses in zone 2 and higher are closed to testing.
 - c. If more than two of the six patients (>2/6) experience DLT, then we close dose level 1 to testing, and we also close doses in zone 2 and higher.

ii) Study Procedure

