Subjects will be expected to take the dose combination to which they are as assigned and as prescribed. Subjects will record dates and times each medication dose was taken on their log forms which will be collected weekly. Subjects will be contact at least weekly by a Research Assistant to monitor symptoms, verify compliance with study drugs and compliance with completing medication logs and daily diary. The Research Assistant will also administer a CAP-SYM 18 during this call. The Research Assistant will communicate any concerns and all findings to a study Investigator who will later call the subject to assess how the subject is doing, discuss any concerns and will monitor the subject in the performance of a 40 Step Test for those subjects provided with an electronic device capable of measuring an Oxygen Saturation level unless the Investigator is concerned about the safety of doing so. Subjects will collect a urine sample weekly. The urine samples and the daily diary and medication log CRFs completed by the subject will be delivered by the subject or a family member within 4 hours of collection by means of the COVID-19 testing car line at Greenville Memorial Hospital. The urine specimens will be sent to Kiyatec® to measure the subject's F2-Isoprostane level, creatinine level, a cytokine panel (IL-1β, IL-2, IL-6, IL-8, IL-10, IFNγ, TNFα and GM-CSF), n-methylhistamine level and TMRSS2 levels. Subjects will self-isolate per current CDC recommendations. Subjects will remain on medication for a minimum of 7 days and unless hospitalized will continue on the medications until it has been more than 10 days beyond the start of symptoms, symptoms have improved and the subject has been without a fever for at least 24 hours without the use of a fever reducing medication. If subjects are hospitalized, then the will instructed to discontinue taking the study medications. After discontinuing study drugs for any reason, the subject will have their blood will be drawn to measure Glutathione level, a cytokine panel (IL-1β, IL-2, IL-6, IL-8, IL-10, IFNγ, TNFα and GM-CSF), and

their tryptase level; and a urine sample will be collected to measure the subject's F2-Isoprostane level, creatinine level, a cytokine panel (IL-1 β , IL-2, IL-6, IL-8, IL-10, IFN γ , TNF α and GM-CSF), n-methylhistamine level and TMRSS2 levels.

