Subjects will be contacted weekly at minimum by the assigned Research Assistant and the assigned Investigator. It will be the responsibility of the assigned Investigator to ensure this happens correctly. Depending how a subject is doing clinically, an Investigator will have the discretion to perform more frequent contacts. These contacts will preferably be done with both a video and audio connection for which the Vivify® devices are capable. A telephonic contact will be discouraged but will be permissible for those who do not have a Vivify® device or for whom an acceptable audio-video connection cannot otherwise be established. Data will be collected and recorded for these contacts on the appropriate REDCap® form, i.e., Research Assistant Weekly Assessment, or Investigator Weekly Assessment. It will be the responsibility of the assigned Research Assistant to enter weekly data from the patient's medication log and daily diaries into the REDCap® forms, Daily Medication Log and Daily Diary. If any new medications are started or any non-trial medications are changed by either the Investigator or any other provider involved in the subject's care as documented in EPIC, the Research Investigator will document such changes using the REDCap® form, New Medications. At the end of every evaluation by the assigned Investigator, the Investigator will document in the REDCap® form their assessment which must be one of the following: 1, Continue on Study Without Change; 2, Have made arrangements for short interval follow-up with myself; 3, Discontinue Study; 4, Recommend Evaluation in ER; 5, Recommend Evaluation by Primary Provider; 6, Recommend Dose Reduction in one or both Trial Medications. If the Investigator Documents any assessment other than "Continue on Study Without Change", an electronic notification will immediately be sent to the PI notifying the PI of the Investigator's Assessment. If the Investigator's assessment is to recommend a dose reduction, they will be directed to document such on the REDCap® form, Trial Drug Adjustment. Within this form, the new dosages will be documented, to include the possibility of discontinuing either or both medications. Additionally, the Investigator will be required to identify whether the adjustment is being made due to a drug toxicity. If the Investigator documents that the adjustment is made due to a drug toxicity upon saving the form an immediate electronic notification will be made to the PI and Chair of the DSMB. The PI will then complete the REDCap form "NCI Adverse Event Serious Adverse Event CTCAE v5." This is an extensive form for which the PI will complete for any AE or SAE. It is comprehensive as it includes the entirety of the CTCAE v5 to include every possible grade of toxicity. Through branching logic, it minimizes the task of data entry only to the particular organ systems or laboratory values involved, an allows the PI to easily document all the data necessary for AE and SAE determination so that the IRB, DSMB and FDA can all be notified as necessary and within the required timelines as described more fully in the "Protection Against Risk" section below.

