
f. Hospital Follow-up Data Collection Process

If a subject becomes hospitalized, the subject's in-patient provider will be notified that the subject was on a clinical trial and of the trial medications the subject was on and any

other pertinent events that occurred while on trial. Also the in-patient provider will be notified of the trial requirement for a final blood draw to measure Glutathione level, a cytokine panel (IL-1 β , IL-2, IL-6, IL-8, IL-10, IFN γ , TNF α and GM-CSF), and their tryptase level; and a urine collection to measure the subject's F2-Isoprostane level, creatinine level, a cytokine panel (IL-1 β , IL-2, IL-6, IL-8, IL-10, IFN γ , TNF α and GM-CSF), n-methylhistamine level and TMPRSS2 levels. These labs will be ordered in EPIC[®] by a study investigator. On a weekly basis the assigned Research Assistant will review the subject's chart in EPIC to review for any of the following: C Reactive Protein blood draw; EKG, Blood Gas; new medications; COVID19 NP swab; supplemental oxygen start or change; intubation; extubation; supplemental oxygen decreased or stopped; ICU admission; ICU discharge; SARS-CoV-2 serum antibody test; and, hospital discharge. A corresponding form for any such event will be completed in REDCap[®].

g. Study Completion Data Collection Process

Upon completion of Study, the REDCap[®] form, Completion Data will be completed.

v) Data Analysis Methods

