The 40 Step Test should only be performed under the direct supervision of a health care provider and for the purposes of this trial will be done during your weekly virtual visit with one of the trial investigators. There is no evidence that this test is harmful; however, its safety has also not been conclusively proven. This test has not been studied previously in patients with a SARS-CoV-2 infection. This test is an exertional desaturation test and a determination will be made by the study investigator at the time of your weekly virtual visit. You will not have to perform this test if you are uncomfortable or unable to do so.

This test will only be administered if you were provided a pulse oximetry device. You will be asked to measure oxygen saturation prior to beginning this test. You will then be asked to walk 40 steps on a level surface, and you will then measure your oxygen saturation after completing your 40 step walk.

Figure of REDCap® Data Entry Forms Mapped by Event

Data Collection Instrument	Enrollment (1)	Post Enrollment (2)	COVID-19 Result - Randomize (3)	Research Labs (4)	Outpatient Follow-up (5)	Hospital Follow-up (5)	Study Completion (7)
Eligibility Assessment Case Report Form	✓						
Demographics	✓						
CURB-65 Case Report Form	✓						
International Prostate Symptoms Score Questionnaire Case Report Form	✓						✓
CAP-SYM 18 Case Report Form	✓				✓		✓
Post Enrollment Checklist	✓						
Baseline Data		✓					
CBC		✓					
BMP		✓					
Coag		✓					
Liver Panel		✓					
C Reactive Protein		✓				✓	
Pregnancy Test		✓					
EKG		✓			✓	✓	
Blood Gas		✓			✓	✓	
PSA		✓					
Starting Medications		✓					
COVID-19 Test Result and Drug Randomization Case Report Form			✓				
Investigator Assignment			✓				
Medication Log							
Trial Drug Adjustment					✓		
Daily Medication Log					✓		
Daily Diary					✓		
New Medications					✓	✓	
Research Assistant Weekly Assessment					✓		
Investigator Weekly Assessment					✓		
Blood Type				✓			
Cytokine Panel				✓			
COVID-19 NP Swab Results						✓	
Hospital Admission						✓	
Supplemental Oxygen Started or Increased						✓	
Intubation						✓	
Extubation						✓	
Supplemental Oxygen Decreased or Stopped						✓	
ICU Admission						✓	
ICU Discharge						✓	
Hospital Discharge						✓	
Completion Data							✓
Antibody Results						✓	
NCI Adverse Event Serious Adverse Event CTCAE v5					✓		

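### After hospital admission, adverse events are captured mainly by passive notification: the CTCAE form is mapped to outpatient follow-up only and the weekly inpatient chart review has no adverse event item

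*Combined protocol and SAP*

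**What the plan says.** Aim 1 makes safety the main question: "The primary outcome is to assess the safety and toxicity profile of the combination of famotidine and oral n-acetyl cysteine". In the Phase I Portion of III) i), "any grade 3 or higher toxicity will be considered a dose-limiting toxicity (DLT"), and the count of subjects with a DLT decides whether a dose is expanded, admitted or closed.

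Section III) iv) e. (Outpatient Follow-up) describes weekly contacts by a Research Assistant and an Investigator. A dose adjustment attributed to toxicity alerts the PI and the DSMB chair and leads to the CTCAE form, of which the section says "This is an extensive form for which the PI will complete for any AE or SAE".

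Section III) iv) f. (Hospital Follow-up) has the Research Assistant go weekly through the subject's "chart in EPIC to review for any of the following: C Reactive Protein blood draw; EKG, Blood Gas; new medications; COVID19 NP swab". The list continues with changes in supplemental oxygen, intubation and extubation, ICU admission and discharge, serum antibody test and hospital discharge, and a corresponding form is completed for each. Before that, "the subject's in-patient provider will be notified that the subject was on a clinical trial and of the trial medications", of pertinent events on trial and of the final samples. No request to report adverse events is stated. Section III) ii) adds: "If subjects are hospitalized, then the will instructed to discontinue taking the study medications".

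In the Appendix figure that maps REDCap forms to events, the row "NCI Adverse Event Serious Adverse Event CTCAE v5" carries one tick, under Outpatient Follow-up.

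**The concern.** Subjects who are admitted are plausibly those most likely to have severe events. Several risks that the protocol lists for famotidine, such as cytopenia, liver injury and rhythm change, are of a kind recognised from inpatient tests. If outpatients are asked about symptoms every week while inpatients depend on someone volunteering a report, the toxicity profile is least complete where events are most severe.

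Escalation could also be affected. With three subjects at a dose level, one unrecorded DLT turns one of three (add three more subjects) into none of three (dose admissible, next zone opens).

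**Working it through.** **1. What happens to active capture at admission**

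- *Form map (Appendix).* The CTCAE row's single tick falls in the fifth of seven event columns, Outpatient Follow-up. I read the position from the column spacing of the extracted text. The header numbers both follow-up columns 5, but they are separate columns with different ticks. EKG, Blood Gas and New Medications are ticked under both, so the map does repeat a form across the two settings where that is intended.
- *Schedule of assessments (Appendix).* The column that holds the weekly assessment forms ends at hospital admission or study completion. The hospital column holds the tracking forms and one set of research samples.
- *Laboratory forms (form map).* CBC, BMP, Coag and Liver Panel are ticked under Post Enrollment only. Inpatient cytopenia or liver injury therefore has no hospital form, and neither is on the weekly review list.
- *Weekly inpatient review (III) iv) f.).* EKG, ICU admission and intubation are covered. Adverse events as such, other laboratory toxicity and death are not. The listed items lead to tracking forms, and the section mentions neither a CTCAE grade nor a causality call for them.

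**2. What still applies in any setting**

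- Under V) ii), the PI completes the CTCAE form within 24 hours of notice of an adverse event, including notice from a research assistant or an outside provider, and immediately if the event is life-threatening or fatal.
- Adverse events include those arising after drug administration, so stopping study drug on admission does not put inpatient events out of scope.
- Changes in severity are recorded as separate events (Duration of AEs).
- Inpatient hospitalization and its prolongation are SAEs.
- The delegation table gives weekly inpatient record review to the sponsor-investigator and clinical co-investigators as well as to research assistants.

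Together: a duty to record exists once someone reports, but in the text available no planned inpatient step is directed at finding and grading adverse events.

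**3. Scale of the effect on escalation**

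The plan gives no figure on this point, so there is nothing to reproduce. For illustration, take one dose level under the modified 3+3 rules of III) i). The next zone opens if there are 0 DLTs in 3 subjects, or 1 in 3 followed by 0 in the next 3. With true DLT rate p and a share m of all DLTs unrecorded, put q = p(1 − m):

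P(open next zone) = (1 − q)³ + 3q(1 − q)² × (1 − q)³

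The 5% and 8% rates are the protocol's assumption in IV) ii). The 30% rate and every value of m are my assumptions.

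Example with p = 0.08 and m = 0.25: q = 0.06, so 0.94³ + 3 × 0.06 × 0.94² × 0.94³ = 0.8306 + 0.1590 × 0.8306 = 0.963.

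| True DLT rate | m = 0 | m = 10% | m = 25% | m = 50% |
|---|---|---|---|---|
| 5% | 0.973 | 0.978 | 0.985 | 0.993 |
| 8% | 0.937 | 0.948 | 0.963 | 0.983 |
| 30% | 0.494 | 0.557 | 0.654 | 0.814 |

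At the assumed rates the shift is at most 0.983 − 0.937 = 0.046, even with half of all DLTs lost. At 30% it is 0.654 − 0.494 = 0.160 with a quarter lost and 0.814 − 0.494 = 0.320 with half lost.

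**The case against.** The strongest reply is that adverse event duties do not depend on setting. The form map shows where a form sits in REDCap; it does not stop the PI from entering an inpatient event. The person who reads the chart each week is a named source of notice, investigators share that review, and an EKG or ICU entry could prompt a report. This stands. A reader might infer that hospital events have no route to the safety data, and the documents do not support that. Nor can one infer that nobody is assigned to find inpatient adverse events, because the later rows of the delegation table were not available to me. The contents of the Hospital Discharge and Completion Data forms were not available either, and they may record death.

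A second reply concerns the 3+3 count, which is of subjects, not events. The severity table in V) ii) grades symptoms that require hospitalization as severe. If that is read as grade 3 and no drug attribution is required, an admitted subject may already count as a DLT, and a later inpatient event changes nothing. This also stands. It narrows the escalation concern to admitted subjects not already counted.

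Finally, a reader might multiply the planned 42 subjects by the 5% to 20% hospitalization range to size the group affected. The documents do not support that product: 42 is the estimate for the escalation period, while the range belongs to the adaptive phase, in a sentence that breaks off in the available text.

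None of these replies supplies active, graded, causality-assessed capture during a hospital stay.

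**Conclusion.** The point holds as a gap in ascertainment. In the documents available, new or worsened inpatient events enter the primary safety outcome mainly when someone volunteers them, whereas outpatient events are sought every week. The likely direction is under-recording of inpatient toxicity. Its size cannot be derived from the documents, which do not give the share of events that would be missed.

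For escalation the consequence is small at the assumed 5% to 8% DLT rate. It becomes material only if a combination is truly toxic and the affected subject was not already counted. The table overstates the likely effect to the extent that m there applies to all DLTs, while this gap concerns only those that arise or worsen in hospital. It does not undermine the design, but it is worth correcting because the outcome is primary and the remedy is nearly free.

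**What to change.** - In the Appendix form map, tick the CTCAE v5 form under Hospital Follow-up and Study Completion as well as Outpatient Follow-up.
- In III) iv) f., add to the weekly chart review: any new or worsened adverse event of any CTCAE grade, including laboratory toxicity, and death. Require notice to the PI, so that the existing 24-hour rule in V) ii) applies. The CTCAE form already covers laboratory values, so no new laboratory form is needed.
- Section III) ii) already keeps the next zone closed until all subjects in the current zone have completed the trial. State there that the inpatient adverse event review is part of that completion; no further hold is needed.

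The cost is two ticks in REDCap, one line in a review already done weekly and one clarifying sentence. The downside is that more events due to COVID-19 itself will be recorded and will need a causality assessment. No dose, schedule or clinical rule changes.

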The main risks to Famotidine which have been occurred in greater than or equal to 1% of subjects in clinical trials are: headache; dizziness; and constipation.

Other adverse reactions that were reported in less than 1 % of subjects in clinical trials include: fever, abnormal weakness or lack of energy; fatigue; heart palpitations; elevated liver enzymes; vomiting; nausea; abdominal discomfort; decreased appetite; dry mouth; decreased platelet counts in your blood; swelling of the tissue around your eyes; rash; eye redness and irritation; difficulty breathing; muscle pain; joint pain; seizure; hallucinations; depression; anxiety; decreased interest in sexual intercourse; difficulty falling asleep; prolonged sleeping; dry skin; flushing; ringing in your ears; altered sense of taste; and difficulty in men with achieving erections capable of intercourse. The following have also been reported during post-approval use of famotidine: changes to your heart by effecting the rhythm in which it beats; jaundice; inflammation and possible damage to your liver; decreased levels of white blood cells, red blood cells or platelets which could be life threatening; allergic reaction which could be life-threatening; rapid swelling of soft tissues often involving tissue around the face, limbs or genitals; hives; muscle damage; muscle cramps; confusion; agitation; tingling, numbness, or burning sensation in the skin often involving hands, feet, arms, or legs; pneumonia; and rash and blistering which could be life threatening.

In a recent prospective trial of patients with Parkinson's disease, doses of famotidine were escalated from 80 mg/day to 120 mg/day to 160 mg/day. No significant adverse effects were observed.¹⁵¹

11. Possible Reduction in Absorption of NAC due to increased Gastric pH

It is conceivable that due to the reduction in gastric pH that oral NAC may not be absorbed as effectively when given in combination. In order to mitigate this theoretical possibility, we have proposed a phase I trial of the combination of the two investigational drugs with twelve possible combinations described in greater detail below. Three arms are with NAC alone. Additionally, while the trial design should allow us to evaluate the possibility of a decreased effectiveness of NAC in combination with FAM, we make the following observations to conclude that it is unlikely that the increased gastric pH will decrease the absorption of NAC.

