The randomization process will be performed using the Randomization module within REDCAP®. This will be performed through use of the data entry form entitled, “COVID-19 Test Result and Drug Randomization Case Report Form.” If the subject has a Rapid Test Performed in the ED and a positive result is obtained prior to discharge, the Co-Investigator who enrolled the subject will be able to access this form and perform the randomization. Otherwise, the randomization will be performed by the PI. Due to the trial design as a Phase I trial, the number of subjects on any arm can vary from zero to six depending on any dose limiting toxicities that may occur. Also, a new zone in the trial will not be able to open until all subjects in the previous zone have completed the trial. Therefore, the randomization process will be dynamic which REDCap® is incapable of handling directly but is capable of handling indirectly in a two-step process as described below. Prior to the start up the trial, a randomization lookup table will be uploaded into REDCap®, which will be nothing more than an ordered table from one to one hundred. While this may seem trivial, it is utterly essential in order to harness the power of REDCap® for a dynamic randomization process. After an investigator has performed the randomization task in REDCap®, the randomization number will be returned from this table. The investigator will then be required to lookup manually the arm to which the subject has been randomized in a file called “Dynamic Randomization Lookup Table” which they will only find within the “File Repository” in REDCap®. An example of this file can be found in the Appendix below. This file will be created prior to the trial initiation by the Lead Statistical Investigator initially assuming three subjects for each trial arm. Anytime, a change is needed to the “Dynamic Randomization Lookup Table” due to a DLT, the PI will suspend the ability for anyone to enroll or randomize a subject through the “User Rights” feature of REDCap® which can be used to restrict access by role to data entry forms. Once a decision has been made about either expanding or closing a trial arm due to a

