Other adverse reactions that were reported in less than 1 % of subjects in clinical trials include: fever, abnormal weakness or lack of energy; fatigue; heart palpitations; elevated liver enzymes; vomiting; nausea; abdominal discomfort; decreased appetite; dry mouth; decreased platelet counts in your blood; swelling of the tissue around your eyes; rash; eye redness and irritation; difficulty breathing; muscle pain; joint pain; seizure; hallucinations; depression; anxiety; decreased interest in sexual intercourse; difficulty falling asleep; prolonged sleeping; dry skin; flushing; ringing in your ears; altered sense of taste; and difficulty in men with achieving erections capable of intercourse. The following have also been reported during post-approval use of famotidine: changes to your heart by effecting the rhythm in which it beats; jaundice; inflammation and possible damage to your liver; decreased levels of white blood cells, red blood cells or platelets which could be life threatening; allergic reaction which could be life-threatening; rapid swelling of soft tissues often involving tissue around the face, limbs or genitals; hives; muscle damage; muscle cramps; confusion; agitation; tingling, numbness, or burning sensation in the skin often involving hands, feet, arms, or legs; pneumonia; and rash and blistering which could be life threatening.

The main risks to N-Acetyl Cysteine include but are not limited to the following: allergic reaction which could be life threatening; rash; itching; nausea or vomiting.

ii) Total Planned Enrollment

Estimated Number of Subjects: 42

We estimate a sample size of around 42 subjects for a 3+3 dose escalation period of our parallel phase I/II trial design. Based on our simulation of the phase I period of the trial and an assumption that a drug limiting toxicity ranges between 5% and 8%, we found an 83% chance that between 27 and 33 subjects would be required. During the adaptive phase of our trial with predicted rates of hospitalization ranging from 20 to 5% as shown in

iii) Does this study involve any of the following: prisoners, pregnant women, children, institutionalized individuals, or other populations that may be considered vulnerable?

No

iv) Does this study seek to exclude a specific racial, ethnic, or gender group? Include a compelling rationale if so.

No

v) Sources of Materials

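### The stated 83% chance of needing 27 to 33 subjects cannot hold for twelve dose combinations: at the plan's own DLT rates it cannot exceed about 54%, and no reading tried gives more than about 15%

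*Combined protocol and SAP*

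**What the plan says.** Section IV.ii (Total Planned Enrollment) gives 42 as the estimated number of subjects and ties it to the escalation period: "We estimate a sample size of around 42 subjects for a 3+3 dose escalation period of our parallel phase I/II trial design". The next sentence gives the simulation result, "we found an 83% chance that between 27 and 33 subjects would be required", under "an assumption that a drug limiting toxicity ranges between 5% and 8" per cent.

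The design is described elsewhere:

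- **Number of arms.** Section II.i.b.11 (on NAC absorption) speaks of "two investigational drugs with twelve possible combinations described in greater detail below. Three arms are with NAC alone". Section III.i (Phase I Portion) crosses four famotidine levels, one of them none, with three NAC levels, and states: "The dose combinations are labelled 1 through 12 and are zoned as illustrated in Figure 10".
- **Cohort size.** In section III.ii (Study Procedure) the randomization table is built "initially assuming three subjects for each trial arm". An arm may end with anything from zero to six subjects.
- **Rules.** Section III.i adds three subjects after one DLT in the first three. On two in three it says: "If two patients (2/3) experience DLT, then we close dose level 1 and all larger doses to testing". After expansion, two DLTs in six leave the dose admissible but "doses in zone 2 and higher are closed to testing"; more than two in six close the dose as well as the higher zones.

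**The concern.** Twelve arms of three make 36, so the whole range of 27 to 33 lies below what the trial needs when every combination is tested and none expands. At a DLT rate of 5% to 8% closures should be the exception, yet the plan gives the range that requires them an 83% probability.

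This is the only simulation result offered for the size of the escalation phase. A reader, including an IRB or DSMB member, would take about 30 subjects as the likely requirement and 42 as leaving at least 42 − 33 = 9 in hand. If the figure does not belong to this design, that margin is not there, and the chance of needing more than 42 is hidden.

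**Working it through.** **Inputs.** K = 12 combinations (II.i.b.11, III.i); three subjects per arm at the start, six at most (III.ii); expansion and closure rules (III.i); DLT probability p = 0.05 to 0.08 (IV.ii). Three DLTs in three is not listed separately and is treated as closing.

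**1. No closures.** An arm expands with probability q = 3p(1−p)², and N = 36 + 3 × Binomial(12, q). N cannot fall below 36, so P(27–33) = 0.

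| p | q | P(36–42) | P(N > 42) |
|---|---|---|---|
| 5% | 0.135 | 78% | 22% |
| 6.5% | 0.171 | 66% | 34% |
| 8% | 0.203 | 55% | 45% |

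**2. A ceiling that needs no zone layout.** N below 36 requires at least one closing outcome: two or more DLTs in the first three, or one in three followed by at least one more in the next three. Per dose,

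c = 3p²(1−p) + p³ + q[1 − (1−p)³].

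- p = 0.05: c = 0.00725 + 0.1354 × 0.1426 = 0.0266. Over twelve doses, 1 − (1−c)¹² = 27.6%.
- p = 0.08: c = 0.01818 + 0.2031 × 0.2213 = 0.0631. Over twelve doses, 54.3%.

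P(27–33) cannot exceed these values, whichever doses a closure removes.

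**3. Simulation of the rules.** Figure 10 is not available, so six zone layouts on the 4 × 3 grid were tried (zone sizes in order):

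- diagonal (1,2,3,3,2,1);
- square (1,3,5,3);
- NAC-alone arms first (3,1,2,3,2,1);
- NAC-alone arms beside famotidine 20 mg, diagonal (2,3,4,2,1);
- the same, square (2,4,6);
- NAC-alone arms last (1,2,3,2,1,3).

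Each was run with closure of all doses at least as high in both drugs and with closure of all later zones, at DLT rates of 5%, 6.5%, 8% and a 5-to-8% gradient. That makes 6 × 2 × 4 = 48 readings, with 200,000 runs each.

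| Quantity | Range over 48 readings |
|---|---|
| P(27–33), stated as 83% | 0.9% to 14.8% |
| P(N < 36) | 12% to 43% |
| P(36–42) | 37% to 73% |
| P(N ≤ 42) | 73% to 87% |
| P(N > 42) | 13% to 27% |
| Median | 39 |
| 95th percentile | 45 to 48 |

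A separate calculation with eight layouts and further closure rules reached at most 15.2%. The median is close to 36 in places: at 8% with later zones closing, P(N ≤ 36) is 0.498 for two of the layouts, and testing one dose at a time gave 36.

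**4. Does another DLT rate rescue the figure?** With a uniform rate anywhere from 1% to 40%, the highest P(27–33) was about 31%.

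**5. What would give 83%?** Nine arms without closures start at 9 × 3 = 27, and two expansions make 33. There P(27–33) is 89%, 84% and 73% at 5%, 6% and 8%. With closures the nine-arm range is 57% to 81%. A simulation that left out the three NAC-alone arms is therefore a possible origin, and adding 3 × 3 = 9 subjects would give 36 to 42. The plan does not say this, and the 83% would not carry over to 36–42 with twelve arms (37% to 73% with closures, 55% to 78% without).

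**The case against.** The strongest objection is that the 15% figure is conditional. The zone figure cannot be read, the rules are written out only for dose level 1, and what counts as a larger dose on a two-drug grid is open. That stands: 15% is the highest value among the readings tried, and the only layout-free ceiling is 54%. But 54% is already well short of 83%, so the missing figure cannot rescue the statement. Nor can the sentence that breaks off at the end of the paragraph. It concerns the adaptive phase, while the phase I sentence is complete.

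It can also be said that little depends on the sentence. The plan says around 42, so this is an estimate and not a cap. The randomization list of one hundred covers the maximum of 12 × 6 = 72, and no dose decision uses the simulated probability. All of this is true and limits the weight of the point. It does not make the sentence correct, and the sentence is the only numerical support given for the escalation size.

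The nine-arm explanation is conjecture. It fits only if closures are ignored and the DLT rate is near 6%. The conclusion does not rest on it.

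**Conclusion.** The concern holds. For the twelve-combination design, an 83% chance of 27 to 33 subjects is impossible at the stated DLT rates: the ceiling is 27.6% at 5% and 54.3% at 8% under any zone layout. Under the written rules and the layouts tried, the probability is about 1% to 15%, and it is zero if no dose closes. The exact value depends on Figure 10 and on how closure is read.

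The planned 42 equals 36 plus two expansions and remains a reasonable planning number. It covers 73% to 87% of runs with closures and 55% to 78% without. The sentence should be corrected because it understates the likely requirement and conceals the chance of exceeding 42.

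**What to change.** Re-run the existing simulation on the twelve-combination grid with the actual Figure 10 zones and the section III.i closure rules, stating the DLT rate used for each dose. Replace the 83% sentence in section IV.ii with: 36 subjects if all combinations are tested without expansion; a maximum of 72; and the simulated P(N < 36), P(36–42), P(N > 42) and 95th percentile. The 42 is then shown with its actual coverage. If the reported simulation covered only the nine famotidine-plus-NAC combinations, say so and still give the twelve-arm result.

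The cost is one re-run and one rewritten sentence. The stated picture becomes less favourable, but the 42 and the dose rules can stay as they are.
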